16.6 Data Collection at 3 Month Follow Up

Patients will be booked in for a 3 month follow-up appointment, as per their standard care pathway. Data collection at 3 month follow up will include completing a patient and observer scar assessment scale (POSAS) with regards to overall scar cosmesis, and also a visual analogue scale (VAS) in relation to suture marks specifically. We have chosen these tools as they are validated, well known scales to characterise scars subjectively and objectively [10].

The patient will be asked about any post-operative complications that were not detected at suture removal including wound infection, dehiscence, and significant post-operative bleeding (defined as bleeding requiring assessment by a healthcare professional). Assessment will be carried out by a member of the research team who will be blinded to trial allocation.

Photographs of the scar will be taken at the follow-up visit using the departmental camera to allow review of scar assessment at a later date if required. This will be directly uploaded onto their electronic patient record in line with Trust policy. Patients will be verbally consented for this at time of follow up, as per usual practice.

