14. AIMS AND OBJECTIVES

Aim:

To test the feasibility of conducting a definitive trial looking at outcomes for earlier removal of percutaneous sutures (7 days versus 10 days) for patients undergoing wide local excision and primary closure for treatment of skin cancers on the chest or back in dermatology.

Objectives:

1. To work out the standard deviation of the outcome measure (suture marks versus no suture marks) in order to estimate a sample size required for a properly powered RCT. (The incidence of 'suture marks' and the impact that these have on patients is currently unknown).
2. To provide some preliminary data on the incidence of wound complications and overall scar cosmesis in each group and ensure that this does not differ from expected:
 - a. *Overall cosmesis*
 - b. *Risk of post-operative bleeding*
 - c. *Risk of surgical site infection*
 - d. *Risk of wound dehiscence (opening up of scar)*
3. To assess the willingness of participants to be randomized.
4. To assess the willingness of clinicians to recruit patients.
5. To assess follow-up rates and adherence.
6. To assess the characteristics and ease of use of the proposed outcome measures including POSAS for scar assessment, a VAS, and patient reported outcome for complications including dehiscence and infection.
7. To gain feedback from patients at their three month follow up appointment on the patient pathway including the trial information leaflet and consent process.
8. To collect data on any additional costs that we may incur that have not been planned for, to inform costing for a future trial e.g. additional printing of PIS or consent forms or additional clinic booking slots
9. To use the gathered data to refine the design of the proposed RCT.

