22.8 Appendix 8 – Data Collection Form

Data Collection Form	
Participant Number:	
Data Collection at Time of Surgery	
Age:	
Ethnicity:	
Clinical diagnosis (pre-op):	
Site:	
Length of wound (mm):	
Width of wound (mm):	
Number and type of interrupted subcuticular sutures:	
Number and type of interrupted percutaneous sutures:	
Drug history (immunosuppressants or anticoagulants):	
Diabetic diagnosis:	
Smoking history:	
History of keloid scar or hypertrophic scarring:	
Normal length of time recommended for suture removal in this case:	

Timing of Suture Removal to Reduce Scarring in Skin Surgery

Data Collection at 3 Month Follow-up			
Stitch marks visible (yes/no):			
POSAS:	Patient scale	Pain:	
		Itch:	
		Colour:	
		Stiffness:	
		Thickness:	
		Irregular:	
		Overall Opinion (not part of total score):	
	Total:		
	Observer Scale	Vascularity (pale; pink; red; purple; mix):	
		Pigmentation (hypo; hyper; mix):	
Thickness (thicker; thinner):			
Relief (more; less; mix):			
Pliability (Supple; stiff; mix):			
Surface area (expansion; contraction; mix):			
Overall Opinion (not part of total score):			
Total:			
VAS:			
Wound infection (defined using CDC criteria for surgical site infection)*:			
Wound dehiscence:			
Significant post-operative bleeding:			
Any other comments:			
* Infection occurs within 30 days after the operation and infection involves only skin and subcutaneous tissue of the incision and at least one of the following: 1.Purulent drainage with or without laboratory confirmation, from the superficial incision 2.Organisms isolated from an aseptically obtained culture of fluid or tissue from the superficial incision			

Timing of Suture Removal to Reduce Scarring in Skin Surgery

- 3. At least one of the following signs or symptoms of infection: pain or tenderness, localized swelling, redness, or heat and superficial incision is deliberately opened by surgeon, unless incision is culture-negative
- 4. Diagnosis of superficial incisional SSI made by a surgeon or attending physician

Timing of Suture Removal to Reduce Scarring in Skin Surgery

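### Infection after suture removal rests on undated, unverified patient recall at 3 months, so the by-arm rates cannot be shown to meet the form's 30-day CDC definition

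*Combined protocol and SAP*

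**What the plan says.** Objective 2 (section 14) asks for preliminary incidence of wound complications in each group, with surgical site infection as item c. Objective 6 lists "patient reported outcome for complications including dehiscence and infection" among the outcome measures to be assessed.

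The form in Appendix 8 has two blocks, one at surgery and one at 3 months. Infection is a single line in the 3-month block: "Wound infection (defined using CDC criteria for surgical site infection". The footnote sets the window, "Infection occurs within 30 days after the operation and infection involves only skin and subcutaneous tissue of the incision", and requires at least one of four criteria:

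1. "Purulent drainage with or without laboratory confirmation, from the superficial incision"
2. "Organisms isolated from an aseptically obtained culture of fluid or tissue from the superficial incision"
3. local signs or symptoms together with an incision deliberately opened by the surgeon, unless culture-negative
4. "Diagnosis of superficial incisional SSI made by a surgeon or attending physician"

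Section 16.6 gives the source at 3 months: "The patient will be asked about any post-operative complications", covering infection, dehiscence and significant bleeding not already found at suture removal. The assessor is blinded (16.6); the patient is not (16.4). At suture removal, the SOP (Appendix 13) has the wound checked for infection and asks for early complications to be notified to the study team. Section 19.1 sends adverse events, infection among them, to R&D once the investigator is aware.

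**The concern.** The definition needs a date and a criterion, and the collection method secures neither. At about 3 months the patient is recalling a window that closed roughly 60 days before. The form does not ask the assessor when the problem began, what was seen, or who diagnosed it. Section 16.6 gives bleeding a definition that a patient can answer (it needed assessment by a health professional), but gives none for infection.

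At stake is what the by-arm infection figure means. Objective 2 wants it compared with what is expected, and section 19.1 wants adverse events watched in both arms. A line that mixes recalled redness, unconfirmed symptoms and diagnosed infection under a CDC label is a poor basis for either, and for choosing a safety outcome for the definitive trial.

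**Working it through.** **The plan's own figures.** The plan states no infection rate, so there is none to reproduce. Its sample size does reproduce: ln(0.05)/ln(0.95) = 58.40, rounded up to 59, and 3/p = 3/0.05 = 60. That p is the probability of an unspecified problem, not an infection rate, and it does not decide this point.

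**Definition against data captured.**

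| What the definition needs | What the plan collects |
|---|---|
| Onset within 30 days | No date field; patient asked at about day 90 |
| Criterion 1, pus | Patient could report it; no field |
| Criterion 2, culture | No field; no record check described |
| Criterion 3, opened incision with signs | Patient might know; no field |
| Criterion 4, clinician's diagnosis | Patient could report it; no field |
| Source of the information | No field; no block for the suture-removal visit |

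A completed line therefore cannot be traced to a criterion or to the window.

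**How much of the window rests on recall.** This takes removal on the allocated day and assumes that the check there finds everything up to that day.
- 7-day arm: 30 − 7 = 23 days, 23/30 = 77%.
- 10-day arm: 30 − 10 = 20 days, 20/30 = 67%.
- Gap from window close to visit: about 90 − 30 = 60 days, taking 3 months as 90 days.

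**Effect of one error.** With 30 analysable cases per group (section 18.4), 1/30 = 3.3 percentage points.

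**Illustration on assumed inputs.** The documents give none of these. Let p be the true 30-day rate, f the share of infections arising after removal, and se and sp the sensitivity and specificity of recall. Infections before removal are taken as all found.

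Recorded rate = p(1 − f) + p·f·se + (1 − p)(1 − sp)

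With p = 0.05 and f = 0.5:
- se = 0.5, sp = 1: 0.025 + 0.0125 + 0 = 0.0375, or 1.1 cases per 30.
- se = 0.8, sp = 0.95: 0.025 + 0.020 + 0.0475 = 0.0925, or 2.8 cases per 30.
- True count: 0.05 × 30 = 1.5 cases.

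Letting f run over 0.25, 0.5 and 0.75, with (se, sp) pairs (0.5, 0.95), (0.5, 1), (0.8, 0.95), (0.8, 0.99) and (0.95, 0.99), the recorded rate spans:

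| Assumed true rate | Lowest | Highest |
|---|---|---|
| 2% | 1.3% | 6.8% |
| 5% | 3.1% | 9.5% |
| 10% | 6.3% | 14.0% |

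**Sampling error for comparison.** One case in 30 has an exact 95% interval of 0.1% to 17.2%.

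**The case against.** Five points can fairly be made for the plan.

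- **The criteria are alternatives.** Pus needs no laboratory confirmation and a doctor's diagnosis is enough, so a patient's account can describe a qualifying infection. This stands. A reader might infer that the rates will fail the definition, and the documents do not support that. They support only that compliance cannot be shown.
- **Recall is not the only route.** The wound is checked at removal, early complications are to be notified, and adverse events are reported once known. This also stands, so it would be wrong to say that infection is found only by asking. But after removal the adverse event route waits for the investigator to hear, and the GP letter (Appendix 12) asks the GP to report nothing.
- **The interviewer is blinded.** This limits interviewer bias but not reporting bias. A reader might infer that misreporting will differ by arm. That is possible because patients know their removal day, but nothing in the documents shows it, and 23 against 20 days of recall is a small difference.
- **Patient report is itself under test (objective 6).** True, but without a reference the study can judge ease of use and not accuracy.
- **The outcome is descriptive.** Section 17 plans no formal comparison, and section 18.4 puts problem detection ahead of estimating frequency. The interval for one case in 30 is wider than any error shown above. This stands and limits the importance of the point. It does not cure the mislabelling, which better recording can remove and which sampling error does not excuse.

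The patient information sheet and consent form were removed from the text reviewed, and the flow chart is not shown. Contact instructions or consent to record access may be there and could not be checked.

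**Conclusion.** The point holds as a mismatch between definition and collection. The infection line carries a 30-day CDC label, yet after day 7 or 10 its only scheduled source is unverified recall at 3 months, with no date, criterion or source recorded. The descriptive rates in objective 2c cannot be shown to meet the label, although some entries may.

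The mismatch itself follows from the texts and needs no assumption. The size does: the 77% and 67% shares take removal on schedule, and the recorded-rate ranges rest wholly on assumed rates and recall accuracy. The main scar outcomes are untouched. It is a modest fault, worth correcting because correction is cheap and because finding such problems before the definitive trial is the study's stated purpose.

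**What to change.** In section 16.6 and on the form:

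1. Keep the question to the patient.
2. Add fields for onset date (within 30 days or not), CDC criterion met, and source (suture-removal report, patient, hospital record or GP record).
3. At the time of the 3-month visit, check the hospital record and GP information for days 0-30 for every patient who reports an infection, and for all participants where access and consent allow. Checking reporters alone can confirm reports but cannot find forgotten infections.
4. Do the check after the scar ratings are completed, so that a removal date seen in the record cannot influence them.
5. Send any GP query after day 30. A reply slip on the enrolment letter (Appendix 12) could come back before the window has closed.
6. Report patient-reported infection and record-confirmed CDC infection separately by arm. This also gives objective 6 a reference for the patient-reported measure.

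The cost is three added form fields and a short record check for up to 60 patients. The documents do not show that the team has access to GP records, so access and consent must be confirmed first. The downside is that mild infections never seen by a clinician will appear only in the patient-reported line.

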We aim to invite patients to join the study who are having a wide local removal of skin on the back or chest. These patients will be randomly assigned to two groups: stitch removal at 7 days and stitch removal at 10 days. The two groups will otherwise be treated the same. Patients will be reviewed again at 3 months to assess their scar and the presence of stitch marks, and to record information about any complications they experienced and information about their experience. This information will be used to assess the feasibility of a larger study to answer the question 'does earlier removal of superficial stitches (7 days rather than 10 days) reduce the risk of stitch marks?'

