16.5 Wound Dressing and Post-operative Care

Following wound closure, the wounds will be dressed with steristrips, a sterile film and pad dressing as per protocol after skin surgery. After 48 hours, the patients will be instructed to remove the dressing and then gently cleanse the wound and apply petroleum jelly to it twice daily until suture removal. This advice will be given to all patients independent on which trial arm they have been allocated.

Timing of Suture Removal to Reduce Scarring in Skin Surgery

On the day of suture removal, either at GP or in the dermatology department, sutures will be removed as per our standard operating procedure (SOP), available in the department or emailed to the GP practice performing the suture removal (please see appendices).

If there are any signs of wound dehiscence, or that the wound may dehisce on suture removal, the suture may be kept in, as per advice on our SOP. These patients will be withdrawn from the study.

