17. DATA ANALYSIS METHODS

[name], Statistical advisor, Royal Devon and Exeter hospital has been consulted.

Data collection and input will be carried out by the research team who will be employed by the RDEFT and will comply with local and national information governance standards. A password-protected Excel spreadsheet will be set up on a Trust computer in the Dermatology Department - also password protected. All paper and electronic data will be collected and stored in compliance with data protection guidelines, good clinical practice in research guidance and Trust clinical governance policy.

A feasibility study will provide an opportunity to assess the data to be collected and the choice of appropriate statistical tests for a future definitive trial. Data analysis will involve statistical methods appropriate to the data collected. The statistical analysis for the feasibility study will be descriptive for each group as hypothesis testing is not an aim of the feasibility study and it is likely to be underpowered for that anyway. Descriptive statistics of baseline characteristics will be compared between study groups to demonstrate the effectiveness of randomisation. Continuous outcome

Timing of Suture Removal to Reduce Scarring in Skin Surgery

data will be tested for normality using the Shapiro Wilks test. If the data are found to be normally distributed, central tendency will be expressed using means and dispersion using standard deviation. If the data prove not to be Gaussian, and cannot easily be transformed, they will be summarized using medians, interquartile ranges and ranges. Mean (or median) differences and the standard deviation of the differences will be used to inform sample size calculations for a definitive trial. Confidence intervals will be derived wherever possible. Categorical data will be summarized as proportions and percentages as appropriate with associated confidence intervals. No attempt will be made at this stage to make formal comparisons of outcome measures – this will be done in the eventual definitive study. Summaries of secondary outcome measures will also be produced in a similar manner to the above.

All data management will adhere to GDPR compliance. Statisticians will be blinded to allocation arms.

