22.13 Appendix 13 – Standard Operating Procedure (SOP) for Suture Removal

Standard Operating Procedure (SOP) for Suture Removal

Aim:

The nurse or healthcare assistant is able to assess the wound post operatively, remove the superficial sutures appropriately and recommend simple post-operative wound care

[figure not shown]
Procedure:

1. Confirm the patients identity and gain consent for removal of sutures
2. Wash hands and prepare procedure trolley surface aseptically with correct equipment:
 - a. Disposable Fine tipped non toothed forceps
 - b. Dressing pack – containing sterile gloves and gauze
 - c. Disposable sharp surgical scissors
 - d. Sterile normal saline if required
3. Wash hands and use non-sterile gloves to remove current dressing (if any)
4. The wound should specifically be checked for signs of dehiscence, infection or poor wound healing. If this is the case, medical advice should be sought
5. If the wound shows signs that it may dehisce if sutures are removed at the time, then consider keeping sutures in for removal at a later date at the discretion of the healthcare professional. These patients will be excluded from the study. If this is the case, it is important that you let the study team know by contacting us on the below details.
6. Removal of simple percutaneous interrupted sutures:
 - a. Wash hands and don sterile gloves
 - b. Gently grasp the knot of a suture with forceps and raise it slightly
 - c. Place the tip of the suture scissors directly under the knot or on the side close to the skin
 - d. Gently cut the suture and pull it out gently across the wound with the forceps
 - i. Remove the suture across the wound to minimise any exposed suture passing through the skin and wound during the removal, this can lead to infection. Cutting the correct part of the suture (part directly under the knot on the side closest to the skin), will bypass this from happening
 - e. Place steri-strips on the sites that sutures have been removed. These are applied in opposite directions with a small amount of tension to take tension away from the wound. Educate patient to let the steri-strips fall off naturally (usually 1-2 days). No further treatment to the wound should be required.

Timing of Suture Removal to Reduce Scarring in Skin Surgery

- f. Continue to remove sutures until all sutures have been removed
- g. The application of a suitable wound dressing can be applied at the healthcare professionals discretion

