- h. Discard sutures as per local policy and record the intervention in the medical notes
- i. Dispose any sharps and used instruments safely according to trust policy

If there have been any early post-operative complications, such as dehiscence, infection or poor wound healing, please could you contact the study organisers on the details below.

[name] (CI), [name] (PI), [name] (PI)
Dermatology Department
Heavitree Hospital
Royal Devon and Exeter NHS Foundation Trust
[name]
[name]
[contact]

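### Does the 3-month complication question in section 16.6 lose events found at suture removal, and lose more of them in the 10-day arm?

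*Combined protocol and SAP*

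**What the plan says.** Section 16.6 words the 3-month question as covering "any post-operative complications that were not detected at suture removal including wound infection, dehiscence, and significant post-operative bleeding". Section 16.4 books removal on day 7 or day 10 according to the allocated arm.

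Other places have no such limit. The lay summary (section 15) says patients will be seen at 3 months "to record information about any complications they experienced". The data collection form (Appendix 8) has plain rows for infection, dehiscence and bleeding in its 3-month part, with a footnoted case definition that begins "Infection occurs within 30 days after the operation". The form has a part for the time of surgery and a part for 3 months, and none for suture removal.

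Events found at removal have their own routes. The suture-removal procedure (Appendix 13) instructs: "The wound should specifically be checked for signs of dehiscence, infection or poor wound healing". It closes with a request: "If there have been any early post-operative complications, such as dehiscence, infection or poor wound healing, please could you contact the study organisers". Section 19.1 lists bleeding, infection and dehiscence among the adverse events, requires adverse events to go to R&D within 24 hours of the investigator learning of them, and commits to recording their incidence in both arms.

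For the analysis, section 17 says: "Categorical data will be summarized as proportions and percentages as appropriate with associated confidence intervals". It does not say where the complication data come from.

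**The concern.** Taken by itself, the wording in section 16.6 ties the scope of the question to a visit that falls three days later in one arm. A complication found at that visit would be outside the 3-month question, and a later visit has had more time to find one. If such events reached the dataset by no other path, both arms would be under-counted, the 10-day arm more so, and the 7-day arm could look worse at equal true risk.

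That would touch objective 2 (section 14), which wants preliminary complication incidence in each group set against what is expected. The lay summary and the form, which carry no limit, make the narrower wording look like an inconsistency, and the missing removal section on the form suggests that early events have nowhere to go.

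A second worry sits beside it. When a wound shows actual or threatened dehiscence at removal, section 16.5 says "the suture may be kept in, as per advice on our SOP. These patients will be withdrawn from the study", and Appendix 13 says "These patients will be excluded from the study". Neither says whether such a patient remains in the dehiscence count of the arm.

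**Working it through.** **The plan's figures.** The plan gives no complication rate and no onset distribution, so there is no stated figure to reproduce. Taken from the documents: 30 analysable patients per group (section 18.4), removal on day 7 or 10 (section 16.4), and a 30-day window for infection (Appendix 8). All other inputs are assumed.

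**Following an early event through the plan**

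1. The person removing the sutures checks the wound (Appendix 13, step 4).
2. If there is a complication, Appendix 13 asks that person to contact the study organisers.
3. Once the investigator knows, section 19.1 treats it as an adverse event and records it by arm.
4. At 3 months section 16.6 asks for what was not picked up earlier. The limit is on detection, not on date: an infection on day 4 that nobody noticed at removal is still asked about.
5. The rows on the form accept an event of either origin.

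The question in step 4 is therefore an addition to steps 1 to 3. The one thing left unwritten is that the two sources are combined in the section 17 proportions.

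**What if the reporting route failed?** Let s be the share of events with onset before removal, d the share of those detected at removal, and f the share of detected events passed on.

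Captured share = 1 − s × d × (1 − f)

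Expected count per arm = 30 × risk × captured share

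Assume a 10% infection risk in both arms, so 3.0 true events per arm. For even onset over days 0 to 30, s = 7/30 = 0.233 and 10/30 = 0.333. For even onset over days 5 to 21, s = 2/16 = 0.125 and 5/16 = 0.3125.

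| Onset | d | f | 7-day arm | 10-day arm | Ratio |
|---|---|---|---|---|---|
| Days 0–30 | 1 | 1 | 3.0 | 3.0 | 1.00 |
| Days 0–30 | 0.5 | 0.5 | 2.83 | 2.75 | 1.03 |
| Days 0–30 | 1 | 0.5 | 2.65 | 2.5 | 1.06 |
| Days 0–30 | 1 | 0 | 2.3 | 2.0 | 1.15 |
| Days 5–21 | 1 | 0 | 2.63 | 2.06 | 1.27 |

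Onset concentrated soon after surgery raises the ratio. With an exponential onset truncated at 30 days, d = 1 and f = 0, a scale of 14 days gives 1.66 v 1.27 (ratio 1.31) and a scale of 5 days gives 0.73 v 0.40 (ratio 1.84). So 1.27 is not a ceiling.

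Across these cases the difference between arms is at most 2.63 − 2.06, about 0.56 of an event (0.56/30 = 1.9 percentage points). The loss within an arm can be larger: 3.0 − 2.0 = 1.0 event in the 10-day arm with even onset over 30 days, and 3.0 − 0.40 = 2.6 events with the 5-day scale.

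For comparison, the 95% Wilson interval for 3/30 runs from 3.5% to 25.6%.

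Every row with f = 0 needs the Appendix 13 contact and the section 19.1 recording to fail for all detected events. Nothing in the documents points to that.

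**The case for a change.** The best case for a change is that the early route is plausible but not secure. Removal may take place at a GP practice, the contact in Appendix 13 is worded as a request, its examples do not name bleeding, and the 24-hour clock in section 19.1 starts only once the investigator knows. No sentence connects either route to the form or to section 17. Within-arm under-counting could also exceed one event if reporting failed. Asking every patient about every complication since surgery would give a second chance to catch what the GP did not pass on.

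Part of this stands. The link between sources is unstated, and complete capture is not guaranteed. But imperfect GP reporting is not caused by the phrase in section 16.6, and the form can already take an early event that a patient mentions. Deleting the phrase has its own costs: longer recall at 3 months, duplicate reports to sort out, and a small added chance that a patient talking about the removal visit reveals the arm to the blinded assessor. Where early reports are merged, deletion changes no count.

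The contrast with the other texts is also weaker than it looks. The lay summary is a general description, and the 30 days on the form are part of a case definition of infection, not the scope of a question put to the patient. That section 17 names no source for complications shows little, since it names none for any outcome.

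The patients withdrawn at removal raise a separate question about withdrawal after randomisation, which does not come from the 16.6 wording. Section 16.5 and Appendix 13 agree with each other, and Appendix 13 asks that the study team be told of these patients, so the event and the participant are known. Only the counting rule is unwritten. Reporting a dehiscence found at removal in the randomised arm is the ordinary course, and it fits objective 2 and the recording promised in section 19.1.

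**Conclusion.** No change to the plan follows. The wording of section 16.6 is narrower than the lay summary and the form, and the merging of early reports with 3-month answers is left implicit. This is a gap that an analyst fills sensibly, by combining the sources and counting each event once per patient in the randomised arm.

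With early events passed on, the distortion is zero. Under an assumed 10% risk and complete failure to pass them on, the arms differ by up to about 0.56 of an event per 30 in the cases tried. That is small beside the uncertainty of a proportion from 30 patients, in a study whose analysis is descriptive and which makes no formal comparison of outcomes. The calculation models infection only and is an illustration, not a bound.

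The conclusion rests on two things: that Appendix 13 and section 19.1 operate as written, and that the material not visible here (the flow chart and the removed appendix pages) does not say otherwise.
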